There is some evidence that clinical decision support (CDS) can be used to improve the utilization rates of clinical decision rules,⁷⁻⁹ but results from these studies are mixed and there is a great need for more high quality studies on the subject.¹⁰⁻¹² Wang et al.,¹³ for example, performed a systematic review and meta-analysis on the impact of pulmonary embolism decision rules on CT use and yield. Out of eight total studies included, there was only one randomized controlled trial and only one of the seven observation studies was rated as high quality. Overall, the authors concluded that implementation of the Wells' Criteria for Pulmonary Embolism through CDS was associated with a modest increase in CT angiography diagnostic yield but there was "a lack of cluster-randomization trials to confirm efficacy of clinical decision rules for pulmonary embolism."¹³

There is also a need for studying novel CDS delivery methods for the recommendation of decision rules. An overwhelming majority of the published studies utilize pop-up alerts,⁷ forced data entry at order placement¹³ or a combination of the two.¹¹ There is evidence, however, that these CDS delivery methods may not be optimal. Westafer et al.,¹⁴ for example, performed a qualitative study looking at provider reported barriers to applying clinical decision rules for pulmonary embolism. Three important barriers they identified were 1) lack of knowledge of rule application 2) timing of the CDS (i.e. too late in the workflow) and 3) alert fatigue. There is a need for implementing and studying CDS methods that address these barriers.

In this study, we plan to evaluate the impact of non-interruptive alerts on the use of clinical decision rules in the emergency department. Providers will be randomly split into an intervention and control groups. The intervention will be patient-specific, non-interruptive alerts suggesting the use of one or more clinical decision rules plus listing the suggested clinical decision rules on the default screen of an EHR-integrated medical reference tool (MDCalc Connect). The alerts will be Epic Storyboard Best Practice Advisory alerts and will include a link for launching the MDCalc Connect app from the alert.

This intervention represents a novel CDS approach that effectively addresses the three aforementioned barriers to clinical decision rule application (lack of knowledge, CDS timing and alert fatigue). In addition, this study will add a randomized controlled trial to an important area of research currently lacking high quality clinical trials.

II. STUDY OBJECTIVE(S); INCLUDING SPECIFIC AIMS AND/OR HYPOTHESES

This study is an extension of a planned quality improvement project that aims to promote standard of care by increasing the use of evidence-based clinical decision rules amongst emergency medicine providers in the University of Utah Emergency Department. Patient-specific information from the EHR will be used to recommend the use of relevant clinical decision rules to emergency medicine providers at the point-of-care. These recommendations will be in the form of non-interruptive alerts with one-click access to the suggested decision rules through the MDCalc Connect EHR add-on application.

To evaluate the efficacy of this quality improvement project, we will perform a cluster randomized controlled trial by splitting participating emergency medicine providers into intervention and control groups. A cluster randomized controlled trial (RCT) study design is necessary for two reasons: 1) there is a great need for RCTs on the study topic (as described in the Background and Significance section) and 2) three clinical decision rules included in the study are related to venous thromboembolic (VTE) disease, and it has been shown that COVID-19 infection increases the rates of VTE. Given the unpredictable and evolving nature of the COVID-19 pandemic, a before-after study design is a poor choice since the rates of VTE will likely be changing over time.

The specific aims are to determine 1) if the patient-specific non-interruptive alerts increase the use of clinical decision rules amongst emergency medicine providers and 2) if an increase in the use of clinical decision rules affects provider ordering habits. The ordering habits of interest will be tests relevant to the specific clinical decision rules included in the study and will be described in detail in the Data Analysis section of this protocol.

III. METHODS

A. Study Design

This study will be a single center, non-blinded, cluster randomized controlled trial. The study site will be the emergency department of a Level 1 trauma center and tertiary referral hospital. It has an annual patient volume of ~60,000 patient visits per year. All resident physicians and advanced practice providers practicing in the emergency department during the study period will be eligible for participation. Eligible participants will be split roughly evenly between intervention and control groups through a stratified random sampling technique. The intervention will be two-part: 1) a non-interruptive alert in the EHR recommending the use of one or more clinical decision rules and 2) a new default tab in the MDCalc Connect app that displays the same clinical decision rules recommended in the non-interruptive alert. Secondary analysis will include retrospective data up to one year prior to study initiation. This historical data will be used as an additional control.

B. Study Population

Provider Participation for RCT: The system will be implemented in the University of Utah Emergency Department. Up to 125 providers could be eligible for trial participation and will include all resident physicians and advanced practice clinicians (APCs) who practice in the role of emergency medicine provider at the study site during the study period. Providers will be split roughly evenly into intervention and control groups as part of a cluster randomized controlled trial. Only providers in the intervention group will receive the recommended decision rule alerts.

Provider participation for retrospective chart review: The same criteria as listed in the RCT description will be used to identify providers for retrospective chart review. This data will be used as a historical control and may include data up to 1 year prior to the RCT study start date. Up to 125 additional providers could meet inclusion criteria.

Patient participation for RCT: All patients evaluated in the University of Utah Emergency Department during the study period with a qualifying chief complaint and age 16 years or old will be eligible for participation in the trial. Up to 10,000 patients could be eligible for participation. The list of qualifying chief complaints was curated by a panel of clinical experts who have extensive experience with the decision rules included in the study. They selected chief complaints based off of likelihood of the chief complaint being relevant to the included clinical decision rules. For example, the Canadian CT Head Rule (which is used for patients with minor head trauma), includes chief complaints such as "fall", "head injury" and "motor vehicle collision."

Patient participation for retrospective chart review: The same criteria as described for the RCT will be used for patients in the retrospective chart review. This data will be used as a historical control and may include data up to 1 year prior to the RCT study start date. Up to 10,000 additional patients could be included in this portion of the study.

C. Assessment of Resources

This study is supported by clinical leadership, and the clinical decision rules selected for inclusion in the study are supported by hospital protocols, clinical leadership or both. We have estimated that a study period of four months will be the minimum duration required to reach statistical power of 0.80 or greater for the study's primary outcome (clinical decision rule usage).

D. Study Procedures

Cluster randomized trial: All eligible providers will be split into intervention and control groups prior to trial initiation using a randomized sampling technique. At study initiation, all providers in the intervention group will receive the clinical decision rule alerts + calculator suggestions in the MDCalc Connect app for all patients that meet inclusion criteria. Providers in the control group will not receive the alerts.

Intervention description: The intervention will contain two components: 1) a non-interruptive best practice advisory (BPA) in the Epic Storyboard and 2) a default suggested calculator tab in the MDCalc Connect app. Six clinical decision rules will be included: Canadian CT Head Rule,

Canadian C-spine Rule, HEART Score, PERC Rule, Wells' PE Criteria and Wells' DVT Criteria. Predefined criteria based on chief complaint, patient age and vital signs will be used to determine when a decision rule may be relevant in a patient encounter. When a patient meets all of the predefined criteria, the intervention will be triggered.

The non-interruptive alert will display in the Epic Storyboard column and will informs the user that a decision rule may be relevant to this patient encounter. For example, it may read "The PERC Rule may be relevant to this patient encounter." A hyperlink to the MDCalc application will be included in the alert. If the provider opens the MDCalc application, the recommended decision rule(s) will be displayed on the app home page. The function of the MDCalc app will otherwise be unaffected and the provider may use the app in its usual way.

The decision rules selected are supported by the American College of Emergency Physicians and the study site medical director leadership team and are considered standard of care. Use of the decision rules is expected to improve the quality of patient care and diagnostic yield of imaging studies and decrease the radiation exposure and cost of care for patients. The intervention alerts are not expected to impact any providers at the study site other than the providers participating in the study.

IV. DATA COLLECTION

Following the trial, data for analysis will be extracted from the University of Utah data warehouse, system logs and MDCalc Connnect application logs. This will include data for the RCT and the retrospective chart review, which will include identical inclusion criteria and outcomes as the RCT with a study period up to 1 year prior to RCT initiation. The outcome measures and the analysis approach are described in detail in the Data Analysis section.

V. DATA ANALYSIS

All primary and secondary outcomes will be compared between the intervention group and control group. Retrospective data up to one year prior to RCT initiation may be included as a historical control.

Alert-related outcomes: The primary outcome is the proportion of times a decision rule alert resulted in use of the decision rule by the provider in the MDCalc Connect app. This will be a composite calculation of all the individual clinical decision rules included in the study. The proportion of uses of individual clinical decision rules will serve as secondary outcomes and are listed below:

- Canadian CT Head Rule
- Canadian C-spine Rule
- HEART Score
- Wells' Criteria for Pulmonary Embolism
- PERC Rule for Pulmonary Embolism
- Wells' Criteria for DVT

We plan to include additional alert-related secondary outcomes such as app usage measures from the MDCalc Connect app logs (e.g. total app usages across the institution, total app usages for providers participating in the study, etc.). The same app usage measures from one year prior to the study period will also be analyzed as historical controls.

Process outcomes: The following process measures related to the decision rules will be included as secondary outcomes to analyze if/how the alerts and decision rule use affected provider test ordering habits.

1. Advanced imaging studies: Number of advanced imaging studies ordered that are relevant to decision rules included in the study. Specific advanced imaging studies will include: CTA chest w/ IV contrast, CT chest w/ contrast pulmonary arteries for pulmonary embolism, Head CT without IV contrast, CT C-spine without IV contrast and lower extremity duplex venous scans.
2. Laboratory tests: Number of lab tests completed relevant to the decision rules alerts. Specific lab tests will include: d-dimer and troponin.

Patient outcomes: The following patient outcomes will be included as secondary outcomes to analyze if/how the decision rule alerts affected clinical care:

- 30-day emergency department bounceback rates (i.e. a return ED visit within 30 days)
- Admission rates

Statistical power:

To estimate statistical power, we developed a simulation in R. We made the following assumptions for these calculations: 1) the number of eligible providers and patients will be ~50 and ~4000 (respectively) in a 4-month study period 2) the MDCalc Connect app use rate will increase from a baseline of 5% to 20% with the decision rule alert intervention and 3) the intra-class correlation coefficient (ICC) is 0.3. The ICC estimate was based off of published literature on the subject.¹⁵ All the estimated statistical powers were calculated based on two-sided t-tests with a significance level of alpha = 0.05. With a 4-month study period, we estimate more than 82% power to detect a difference between the intervention and control groups for the primary outcome (calculator usage).

VI. DATA AND SAFETY MONITORING PLAN (if applicable)

Not applicable.

VII. STUDY LIMITATIONS

The primary limitation of this study is that supervising (“attending”) physicians are not included in the randomization. Due to the staffing design at the study site, it was impossible to design a randomized controlled trial that included all providers (attendings, residents and ACPs). As such, attending physicians were excluded. Given that decisions are typically made jointly between the

attending and junior team member (resident or APC), we suspect this may impact the results of this study.

VIII. ETHICAL CONSIDERATIONS

Informed consent for participating providers and patients has been waived by the University of Utah IRB Committee. The risks for this study are considered no more than minimal. Benefits include: improved quality of patient care, improved diagnostic yield of imaging studies and decreased the radiation exposure and cost of care for patients. There will be no financial costs to study participants and no compensation will be provided.

IX. PLANS FOR DISSEMINATION OF FINDINGS

Findings will be submitted to a peer-reviewed journal upon study completion.

X. REFERENCES

2. American College of Emergency Physicians. American College of Emergency Physicians: Ten Things Physicians and Patients Should Question. Choosing Wisely. Published 2014. <https://www.choosingwisely.org/societies/american-college-of-emergency-physicians/>

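### The ordering and patient outcomes have no planned adjustment for complaint, age or vital signs, which gives up precision, mainly for troponin and head CT

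*Combined protocol and SAP*

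**What the plan says.** Section V (Data Analysis) states that "All primary and secondary outcomes will be compared between the intervention group and control group". For the process and patient outcomes it goes no further: it gives no regression model, no covariate and no method for clustering. The only test named anywhere is the two-sided t-test in the power paragraph, which concerns the primary outcome. The imaging and laboratory outcomes are counts, for example "Number of lab tests completed relevant to the decision rules alerts", with no stated denominator.

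Section III.D, on the intervention, says that "Predefined criteria based on chief complaint, patient age and vital signs will be used to determine when a decision rule may be relevant". Appendix A lists the qualifying complaints by rule, from falls and motor vehicle crashes to chest pain and leg swelling.

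Section III.A describes the design: "This study will be a single center, non-blinded, cluster randomized controlled trial". It adds that "Eligible participants will be split roughly evenly between intervention and control groups through a stratified random sampling technique", without naming the strata. The documents do not say how patients come to be assigned to providers.

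**The concern.** Providers are randomised and patients are not; patients reach a provider after allocation. Whether a troponin, a d-dimer or a head CT is ordered depends heavily on why the patient came and how old the patient is. Differences between providers in the complaints they see therefore add noise to any comparison of ordering that leaves complaint out.

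These outcomes carry aim 2 (whether rule use changes ordering) and the question about clinical care, and no power is given for them. Any effect is likely to be small. The power paragraph expects use to rise from 5% to 20%, which is 15 extra uses per 100 encounters. If 10-30% of those changed an order (an assumption), the effect on ordering would be 15 x 0.10 = 1.5 to 15 x 0.30 = 4.5 points per 100 encounters. At that size, avoidable noise matters.

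**Working it through.** **1. The plan's own figure.** Section V assumes "the number of eligible providers and patients will be ~50 and ~4000 (respectively) in a 4-month study period", which is about 25 providers per arm with 80 patients each, and an ICC of 0.3.
- Design effect: 1 + 79 x 0.3 = 24.7. Effective n per arm: 2000/24.7 = 81.0.
- For 5% v 20% with two-sided alpha 0.05: z = [0.15 x sqrt(81.0) - 1.96 x sqrt(2 x 0.125 x 0.875)] / sqrt(0.05 x 0.95 + 0.20 x 0.80) = (1.350 - 0.917)/0.456 = 0.95, so power is 82.9%.

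The stated figure of more than 82% reproduces, but it covers the primary outcome only.

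**2. Assumptions for the ordering outcomes.** None of these is in the documents.
- Complaint mix: 40% chest/dyspnoea, 50% head/neck, 10% leg.
- Rates in those groups: troponin 75/10/5%; head CT 5/50/1%; d-dimer 30/2/20%; admission 35/20/15%.
- Between-provider SD of practice, s: 5 or 10 points.
- SD of a provider's chest-complaint share: 0 (mix varies only by sampling) or 10 points.

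**3. Formula.** Let B be the between-complaint variance of the outcome, W the within-complaint variance, and f = SD²/(0.4 x 0.6) the case-mix ICC implied by the chest-share SD. A provider mean has variance s² + W/80 + C, with C = B x [f + (1 - f)/80]. Adjusting for complaint group removes C, so the variance cut is C/(s² + W/80 + C).

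**4. Troponin.** The mean is 0.355.
- B = 0.4 x 0.5625 + 0.5 x 0.01 + 0.1 x 0.0025 - 0.355² = 0.1042.
- W = 0.4 x 0.1875 + 0.5 x 0.09 + 0.1 x 0.0475 = 0.1248, so W/80 = 0.00156.
- Share SD 0: C = 0.1042/80 = 0.00130. Share SD 10 points: f = 0.01/0.24 = 0.042 and C = 0.00559.
- s = 5 points: 0.00130/(0.0025 + 0.00156 + 0.00130) = 24%; 0.00559/(0.0025 + 0.00156 + 0.00559) = 58%.
- s = 10 points: 0.00130/(0.01 + 0.00156 + 0.00130) = 10%; 0.00559/(0.01 + 0.00156 + 0.00559) = 33%.

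**5. All four outcomes.** Simulation keeps probabilities between 0 and 1, which trims the practice effects, so its cuts tend to be slightly larger than the formula's. Ranges run from share SD 0 to 10 points and cover the simulations and, at 10 points, also the formula.

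| Outcome | Variance cut, s = 5 points | Variance cut, s = 10 points |
|---|---|---|
| Troponin | 28-60% | 10-38% |
| Head CT | 14-42% | 5-23% |
| D-dimer | 5-24% | 1-8% |
| Admission | 1-9% | 0-3% |

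In the most favourable of these settings (troponin, s = 5, share SD 10) the 95% half-width falls from about 5.3 to 3.4 points. Return visits were not modelled.

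**6. Validity.** A separate null simulation used a 50% share of a high-ordering complaint, a 30% mean ordering rate, an ordering gap of 20 or 40 points, practice SD of 3-10 points and case-mix ICC of 0-0.2.
- The unadjusted provider-level t-test had a type I error of 4.7-5.2%, the same as the adjusted one.
- Unadjusted intervals were 1-9% wider at case-mix ICC 0 and 5-59% wider at 0.1.
- The 1-SD chance shift is gap x sqrt(2 x 0.25 x (1 + 79 x ICC)/2000). That is 0.3-0.6 points at ICC 0 and 0.9-1.9 points at 0.1.
- A patient-level test ignoring clustering gave 9-47% false positives.

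**The case against.** A reader might infer that the plan has chosen an unadjusted analysis and that case mix could pass for an alert effect. The documents support neither. Section V is silent on method and does not rule out adjustment. Chance imbalance under provider randomisation is ordinary sampling error, which a provider-level test already counts. A systematic imbalance would need patient pick-up to differ by arm. The design leaves that possible, but nothing in the documents shows it, and adjustment for measured variables would not remove differences in unmeasured severity.

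The size is also open to challenge, and this stands. A practice SD of 5 points corresponds to an ICC of about 0.0025/0.229 = 0.011 for troponin. At an ICC of 0.1 the troponin cut is 5-19%, and at 0.3 it is 2-7%. The plan's 0.3 was assumed for app use, not ordering, so it does not settle the matter. If each test were analysed only within its own complaint group, complaint would matter less. Age alone would then still give a cut of 11-20%, under an assumed contrast of 50% v 85% tested.

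Section III.B says "Up to 125 providers could be eligible for trial participation" and "Up to 10,000 patients could be eligible for participation", so 25 per arm is the power assumption and not a fixed number. More providers would shrink chance imbalance. Stratification may help too, but its factors are unnamed, and strata set on providers before the trial cannot directly balance the patients each later sees.

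**Conclusion.** The point holds as one about precision on secondary outcomes, and it is worth acting on because those outcomes are the evidence for aim 2. Baseline variables that the trigger already uses are left out of the planned analysis. Under the assumed rates and mix, the gain from using them is material for troponin and head CT when providers' practice varies by about 5 points. It is more modest at 10 points and falls further beyond that. It is small for d-dimer, negligible for admission and not shown for return visits. Every one of these sizes depends on ordering rates, complaint mix and provider spread that the documents do not give.

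The documents do not support a finding of bias or of an inflated false-positive rate from omitting case mix, provided the comparison is made at provider level. The residual exposure is to measured case-mix differences if pick-up differs by arm, which the plan does not address.

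**What to change.** In Section V, express the imaging and laboratory outcomes per eligible encounter. For these, and for consistency for admission and return visits, name as the main analysis one that respects clustering by provider. Adjust it for chief-complaint group (Appendix A), age, vital signs recorded before provider contact, and the randomisation strata. Either of two methods would serve:

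- A two-stage analysis: fit an encounter-level regression on the covariates without arm, then compare provider means of observed minus expected between arms, allowing for strata.
- A mixed model or GEE with a small-sample correction.

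Report the unadjusted provider-level comparison as a sensitivity analysis. The cost is a few lines of text and a little more analysis work, with little return for admission. No new data collection is needed.

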Motor Vehicle Crash
Motorcycle Crash
Motorcycle vs pedestrian
LOC (loss of consciousness)
Head Injury
Headache - Injury

Head injury - closed
Trauma
Canadian C-spine
Fall
Motor Vehicle Accident
Motor Vehicle Crash
Motorcycle Crash
Motorcycle vs pedestrian
Neck pain - injury
Neck injury
Trauma
HEART Score
Chest Pain
Chest pressure
Shortness of Breath
Breathing Problems
Difficulty breathing
Wells' PE Criteria and PERC Rule
Chest Pain
Shortness of Breath
Breathing Problems
Difficulty breathing
Hypoxemia
Hemoptysis
Wells' DVT Criteria
Leg Pain
Deep Vein Thrombosis
Leg Swelling
Swelling, Lower Extremity
Leg Pain - Other
